6.2.2. Analysis of secondary endpoints

- Linear regression with interaction will be used to assess magnitude of change in effect of atorvastatin on CIMT associated with baseline CMV copy number
- For other continuous endpoints, a 2 sample T-test

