3. STUDY ENDPOINTS

3.1. Primary endpoint

The mean or median CIMT changes of virally suppressed HIV patients with CMV seropositivity in atorvastatin group versus placebo group between baseline and week 48

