3.2. Secondary endpoints

1. Magnitude of change in effect of atorvastatin on CIMT associated with baseline CMV copy number
2. The mean or median changes of fasted lipid between baseline and week 24, week 24 and week 48

3. The mean or median changes of brachial artery flow mediated vasodilatation (FMD) between baseline and week 48
4. The mean or median changes of liver fibrosis and steatosis in atorvastatin and placebo group between baseline and week 48
5. The mean or median changes of sCD14, VCAM, ICAM, CRP, and β 2M in atorvastatin and placebo group lipid between baseline and week 24, week 24 and week 48
6. The mean or median changes of neurocognitive function in atorvastatin and placebo group lipid between baseline and week 24, week 24 and week 48
7. The mean or median changes of oral periodontitis score in atorvastatin and placebo group between baseline and week 48
8. Magnitude of change in effect of atorvastatin on FMD, neurocognitive function, liver fibrosis and steatosis, lipid profile, and immune activation biomarkers associated with baseline CMV copy number

[figure not shown]

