4.5. Population and Sample Size

Target population is HIV-positive patient on stable ART routinely controlled in HIV Integrated Care Unit Cipto Mangunkusumo Hospital, Jakarta.

Assuming that the effect size is 0.1, standard deviation is 0.12, and the use of 2 sample t-test, the sample size needed for 90% power and 5% significant level is 32 per arm. With additional 20% drop, each arm (placebo and control group) will need 40 participants.

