6.2.1. Analysis of primary endpoints

T test will be used to compare the mean CIMT changes of virally suppressed HIV patients with CMV seropositivity in atorvastatin group versus placebo group between baseline and week 48.

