APPENDIX B. OPERATIONAL DEFINITION

{Operational definition table, please describe the main variables and how to measure them.}

Variable	Operational Definition	Measurement
CIMT changes	Numerical changes (in millimeter) between baseline and 48 weeks CIMT	Common Carotid Artery (CCA) intima media thickness measured by using B mode imaging system, equipped with a linear array transducer > 7 MHz with minimal compression (<10:1) and footprint of at least 3 cm (https://www.escardio.org/Journals/E-Journal-of-Cardiology-Practice/Volume-13/Intima-media-thickness-Appropriate-evaluation-and-proper-measurement-described)
FMD changes	Numerical changes (in percentage) between baseline and 48 weeks FMD	Using a high-resolution ultrasound linear array transducer, longitudinal images of the right brachial artery (mostly 3-15 cm above the elbow) were recorded at the baseline and for 3 minutes after cuff deflation following suprasystolic compression (50 mmHg over the systolic blood pressure) of the right forearm for 5 minutes. https://www.jstage.jst.go.jp/article/ihj/advpub/0/advpub_17-013/_pdf ; EHJ 2010. 2854-61 Assesment of atherosclerosis : the rolw of FMD
Liver fibrosis change	Numerical changes (in KPa) between baseline and 48 weeks	The measurement of liver stiffness which uses the velocity of shear waves that travel through the liver using the Fibroscan (Echosens) device
Liver steatosis change	Numerical changes (in dB/m) between baseline and 48 weeks	The measurement of steatosis using the Fibroscan (Echosens) equipped with CAP software. dB/m

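### Endpoints are worded as mean or median change, but the only planned test is an unadjusted t-test of means: valid, but inefficient for right-skewed biomarkers

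*Combined protocol and SAP*

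**What the plan says.** Section 3.1 defines the primary endpoint as "The mean or median CIMT changes of virally suppressed HIV patients with CMV seropositivity" in the two groups from baseline to week 48. Section 6.2.1 then settles on one of the two: "T test will be used to compare the mean CIMT changes".

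Section 3.2 uses the same either-or wording for lipids, FMD, liver fibrosis and steatosis, neurocognitive function and the periodontal score. It does so too for the inflammatory markers: "The mean or median changes of sCD14, VCAM, ICAM, CRP" and beta-2-microglobulin, over two intervals (baseline to week 24, and week 24 to week 48). The synopsis repeats this in its endpoint rows.

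Apart from the CMV interaction model, section 6.2.2 has one line for all of these: "For other continuous endpoints, a 2 sample T-test". Sections 6.2 to 6.2.3 mention no transformation, distribution check, rank method, covariate or rule for choosing between mean and median.

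Appendix B defines CIMT change as "Numerical changes (in millimeter) between baseline and 48 weeks CIMT". It defines FMD, liver stiffness and CAP change likewise as numerical differences. It does not list the biomarkers or lipids.

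**The concern.** The endpoint wording foresees data for which a median would be the better summary, but the analysis section supplies only a comparison of means. If medians were reported for a marker, no pre-specified test would stand behind them.

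The second issue is efficiency. If change is taken on the measured scale, a few participants with high baselines dominate the variance of a right-skewed marker. The baseline value is collected but not used as a covariate. Secondary objective 6 looks for an effect on sCD14, VCAM, ICAM, hsCRP and beta-2-microglobulin, and the synopsis rationale names an anti-inflammatory action as one possible route of benefit. The sample size was set for CIMT alone, so power for these markers is whatever the method leaves. A null result from an inefficient analysis could be misread as evidence against that route.

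**Working it through.** **The plan's own figure.** Section 4.5 gives a CIMT difference of 0.1, an SD of 0.12, 90% power and a 5% level. The normal formula is n = 2(1.960 + 1.282)²(0.12/0.1)² = 2 × 10.51 × 1.44 = 30.3, so 31 per arm. The exact t calculation gives power 0.898 at 31 and 0.907 at 32, hence the stated 32. Then 32/(1 − 0.20) = 40. The figure reproduces (two-sided), but it concerns CIMT only.

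**Assumed inputs for a biomarker.** The documents give none. I take a log-normal marker, 32 per arm, a correlation of 0.7 between log baseline and log follow-up, a log-scale SD σ from 0.2 to 1.2, and a multiplicative treatment effect. All tests are two-sided at 5%.

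**Hand check at σ = 1.0 and a 40% reduction** (ratio 0.6, ln 0.6 = −0.511, baseline median set to 1):

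- Untransformed change. The difference in mean change is 0.4 × e^0.5 = 0.659. The baseline variance is e(e − 1) = 4.671 and the covariance with follow-up is e(e^0.7 − 1) = 2.756. The variance of change is 2(4.671) − 2(2.756) = 3.83 on placebo, and 4.671(1 + 0.36) − 2(0.6)(2.756) = 3.05 on atorvastatin. SE = √((3.83 + 3.05)/32) = 0.464, so z = 1.42.
- Log change. SD = σ√(2(1 − 0.7)) = 0.775; SE = 0.775√(2/32) = 0.194; z = 2.64.
- Log ANCOVA. SD = σ√(1 − 0.7²) = 0.714; SE = 0.179; z = 2.86.

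Subtracting 1.96 gives approximate power of 30%, 75% and 82%. The normal approximation is rough for the first, because the t statistic is far from normal with such tails, so simulation is used below.

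**Simulated power** (40,000 replicates per row, Monte Carlo SE at most 0.25 percentage points):

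| Log SD | Reduction | t-test, untransformed change | t-test, log change | Log ANCOVA | Power lost, first vs last |
|---|---|---|---|---|---|
| 0.2 | 10% | 72.6% | 76.3% | 82.1% | 12% |
| 0.5 | 30% | 83.2% | 95.3% | 97.5% | 15% |
| 0.5 | 40% | 97.2% | 99.9% | 100% | 3% |
| 0.8 | 40% | 58.6% | 89.6% | 93.6% | 37% |
| 1.0 | 40% | 35.9% | 74.1% | 80.0% | 55% |
| 1.2 | 40% | 22.3% | 58.6% | 64.5% | 65% |

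The last column is 1 minus the ratio of powers; for example, 1 − 35.9/80.0 = 55%. At a correlation of 0.5 and a 40% reduction the loss is 48% at log SD 0.8 (42.2% versus 81.8%) and 60% at 1.0 (25.3% versus 63.6%). So a loss above half needs a log SD of about 1.0 or more.

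**Source of the gain.** At log SD 1.0 most of it is the scale: 38 of 44 percentage points. At log SD 0.2 most of it is baseline adjustment: 5.8 of 9.5 points.

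**Type I error.** With no treatment effect, the t-test on untransformed change rejects in 3.8–5.2% of replicates for log SD 0.2 to 1.2. It is not inflated.

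**The case against.** The strongest reply is that the plan does pre-specify its test. Sections 6.2.1 and 6.2.2 name a t-test, that test holds its level, and no power is claimed for any secondary endpoint. All of that stands.

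A reader might go further than the documents allow in three ways.

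- **That the analysis will be chosen after seeing the data.** If the smaller p-value of a t-test and a Wilcoxon test were reported, the error rate on skewed data would be 6.2–6.8% per comparison. That would mean departing from the written analysis. The looseness is in the endpoint wording, not in the test.
- **That the biomarker analyses lose more than half their power.** No biomarker SD, distribution, correlation or effect size is given, so this cannot be shown for any of the five markers. For mildly skewed markers the loss is modest.
- **That the plan prescribes the measured scale for biomarkers.** This is inferred from silence and from the numerical-change definitions in Appendix B, which omit the biomarkers.

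It is also fair that a ratio of geometric means answers a somewhat different question from a difference in mean change, and that part of the gain comes from baseline adjustment, not from handling skewness. Neither removes the benefit: the baseline is already collected, and log-scale ANCOVA was at least as powerful in every row of the table.

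**Conclusion.** The point holds as a mismatch of wording and an avoidable loss of efficiency. The endpoint sections allow a median for which no method exists, and the one method given uses neither a log scale nor the baseline as covariate. With 32 per arm and a correlation of 0.7, power falls from 82% to 73% in the mildest case examined and from 80% to 36% at an assumed log SD of 1.0. Where any particular marker lies in that range cannot be settled from the documents.

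The planned t-test is not invalid. The power argument does not touch the primary CIMT comparison: there only the wording of section 3.1 disagrees with section 6.2.1, which already settles on the mean. These are secondary endpoints, so the change is advisable and does not threaten the main result.

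**What to change.** 1. Remove the median option from section 3.1, section 3.2 and both endpoint rows of the synopsis, so that they match the tests of means. For the markers in item 2, say that the mean is a geometric mean.
2. In section 6.2.2, state that hsCRP, sCD14, VCAM, ICAM, beta-2-microglobulin, triglycerides (within the fasted lipid profile) and liver stiffness are analysed on the log scale by ANCOVA, with treatment group and the log baseline value as covariates. Do this at week 24 and at week 48; liver stiffness is measured only at baseline and week 48. The Appendix A schedule shows lipids at screening and not at randomisation, so name the screening value as the lipid baseline.
3. For the week 24 to week 48 change in section 3.2, use the log week-24 value as covariate and label the comparison as conditional on a post-randomisation value.
4. Report ratios of geometric means with 95% CI, and align the liver stiffness entry in Appendix B, which now gives a numerical change in kPa.

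I would not add a rank method for the periodontal score here, because the documents do not define that score's scale.

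The cost is wording, made before unblinding, with no extra data, visits or participants. The downside is that effects on these markers are reported as ratios and not as absolute differences.

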6.2.3 Missing data plan

We will compare subject characteristics in the drop out with remaining participants. If there is no different of the characteristic, we assume that the missing is at random.

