4.6.3 Drop Out Criteria

1. Pregnant during this study
2. Stop using ART > 1 month
3. Stop or refuse to use atorvastatin during this study
4. Not willing to continue as participant in this study

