4.11. Study Intervention

4.11.1. Study drug and dosage:

- Atorvastatin 20 mg tablets in generic form
- The placebo tablets will be prepared by Cipto Mangunkusumo hospital pharmacist, were composed of starch and were similar to atorvastatin tablets in size, shape, and colour.

4.11.2. Treatment administration:

The administration of study drug is home-based participant self-administration. The participants will get the medication after randomization process (week – 0) at least 1 week after. The participants will get supply every month along with the refill of antiretroviral drugs. The drug and placebo tablets will be administered to patients by a staff member who are privy to the treatment. In the end of every month, each participant should return the unused pills every month. All prescriptions will use hospital Electronic Medical Record system.

4.11.3. Drug interaction:

During this study, each participant is not allowed to use cyclosporin, fenofibrate, and rice yeast herbal supplements.

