4.13. Study Schedule and Procedures

Each participant will be followed for one year after start using study drug.

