4.13.3. Follow Up Visit(s)

Patient will be seen for regular clinical follow up as standard of care in the clinic (monthly/ bimonthly). Follow up visit will include clinical and laboratory procedure as presented in table study schedule (appendix).

At week 24, blood collection procedures and neurocognitive examination procedures will be repeated. At week 48, blood collection procedures, CIMT, FMD, transient elastography with CAP, neurocognitive examination, and community periodontal index procedures will be repeated.

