6.2. Statistical Consideration & Analysis Plan

Subjects will be analyzed in the group to which they were randomized, regardless of the treatment received.

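### The missing-data rule infers missing at random from a check that cannot show it, and no sensitivity analysis is planned; the likely bias is modest, but results just above the significance threshold would be exposed

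*Combined protocol and SAP*

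**What the plan says.** Section 6.2.3 is the whole missing-data plan. Drop-outs are compared with remaining participants, and: "If there is no different of the characteristic, we assume that the missing is at random". It does not name the characteristics, a criterion for a difference, a comparison by arm, a method of analysis, or what follows if a difference is found. No sensitivity analysis appears anywhere in the document.

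The primary analysis (section 6.2.1) is: "T test will be used to compare the mean CIMT changes of virally suppressed HIV patients", from baseline to week 48. Section 6.2 adds: "Subjects will be analyzed in the group to which they were randomized, regardless of the treatment received". Neither says how a participant without a week-48 CIMT enters the analysis.

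CIMT is taken only at baseline and week 48. For the interim visit, section 4.13.3 says: "At week 24, blood collection procedures and neurocognitive examination procedures will be repeated". The sample size allows for loss (section 4.5): "With additional 20% drop, each arm (placebo and control group) will need 40 participants".

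Three places bear on participants who stop study drug. Section 4.6.3 lists as a drop-out criterion "Stop or refuse to use atorvastatin during this study". Section 4.13 says "Each participant will be followed for one year after start using study drug". Section 9.6 treats stopping treatment and leaving the study as separate events.

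**The concern.** Missing at random is a statement about the unobserved week-48 CIMT, given what has been observed. Similar baseline characteristics do not establish it, because the unseen outcomes may still differ. Dissimilar characteristics do not refute it, because the assumption allows missingness to depend on observed data. The rule therefore ties the assumption to evidence that bears on it in neither direction, and leaves the method open if a difference is found, which invites a choice after the data are seen.

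A participant who leaves before week 48 has only a baseline CIMT, so the t-test has nothing to use for that person. If loss is related to outcome and differs between arms, the estimated difference is biased and the planned check would not show it. At stake is how a significant primary result near the threshold can be read.

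**Working it through.** **Inputs.** Section 4.5 gives a difference of 0.1, SD 0.12, 90% power, 5% significance, 32 per arm, and 40 per arm with 20% loss. It gives no units; Appendix B measures CIMT change in millimetres, and I assume mm throughout. A positive difference means benefit of atorvastatin. The documents give no drop-out figures by arm or by outcome, so the drop-out patterns below are assumptions.

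**The plan's own figure.** A two-sided t-test with standardised difference 0.1/0.12 needs 31.25, so 32 per arm (power 90.7%). Then 32/(1 − 0.20) = 40. Both figures reproduce.

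**Threshold for significance.**
- 20% missing, 32 observed per arm: SE = 0.12 × √(2/32) = 0.0300; critical difference = 1.999 × 0.0300 = 0.060 mm.
- 10% missing, 36 observed per arm: SE = 0.12 × √(2/36) = 0.0283; critical difference = 0.056 mm.

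**What the check can detect.** With 16 drop-outs against 64 remaining, a 5% t-test on one characteristic has 19%, 42% and 81% power for standardised differences of 0.3, 0.5 and 0.8. "No difference" is thus weak evidence even about the characteristics.

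**Bias if one arm is selected.** Let a fraction f of the atorvastatin arm be missing, with a mean change worse than that of the observed participants by D, and let placebo loss be unrelated to outcome. The bias is f × D:
- D = 0.05: 0.2 × 0.05 = 0.010 mm
- D = 0.12: 0.2 × 0.12 = 0.024 mm, or 0.024/0.030 = 0.8 of a standard error

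**Rejection rate under no true effect** (60,000 simulated trials, 40 per arm, 8 lost per arm):

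| D (mm) | Selection in atorvastatin arm only | Same selection in both arms |
|---|---|---|
| 0.05 | 6.6% | 5.4% |
| 0.10 | 11.1% | 6.5% |
| 0.12 | 13.9% | 6.9% |

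A normal approximation, Φ(−1.96 + bias/SE) + Φ(−1.96 − bias/SE), gives 6.3% at a bias of 0.010 and 12.6% at 0.024, in fair agreement. With the same selection in both arms the bias is about zero.

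**Does passing the check help?** At D = 0.12 in one arm, with a characteristic correlated 0.3 with CIMT change, the check passes 92% of the time and 14.0% of passing trials still reject. For correlations of 0 and 0.5 it passes 95% and 86% of the time, and 14.0% and 14.2% of passing trials reject. Passing gives no protection.

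**Tipping points.** Shift the missing atorvastatin outcomes by a fixed D. With the SE held at its observed-data value, significance is lost when D = (observed difference − critical difference)/f. At 20% missing and 0.07 mm observed, this is (0.07 − 0.060)/0.2 = 0.05 mm. Delta-adjusted multiple imputation gives somewhat smaller values, because its SE rises with D (0.0303 at D = 0, 0.0329 at D = 0.20):

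| Observed difference (mm) | 20% missing, SE held | 20% missing, imputation | 10% missing, imputation |
|---|---|---|---|
| 0.07 | 0.05 | 0.045 | 0.121 |
| 0.08 | 0.10 | 0.091 | 0.201 |
| 0.10 | 0.20 | 0.176 | 0.344 |

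If participants who stop the drug simply lose its benefit, D is roughly the effect itself. At 20% missing, the tipping D lies below the observed difference at 0.07 mm (0.045 < 0.07) but above it at 0.08 mm (0.091 > 0.08) and 0.10 mm (0.176 > 0.10). At 10% missing it lies above it in all three rows.

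**The case against.** The strongest reply is that the harm is small and the extreme scenario unlikely. Participants, doctors, researchers and outcome assessors are blinded (sections 4.3 and 4.12.2) and the placebo matches (section 4.11.1). Early atherosclerosis gives no symptoms (section 1.1), and CIMT is not rescanned before week 48, so nobody can leave because of their CIMT change. This stands. It makes similar selection in both arms the more plausible case, and that largely cancels. Fortnightly calls (section 4.10) may also keep loss below 20%.

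It is also fair that stopping an ineffective drug cannot worsen CIMT, so that route does not produce the 7% to 14% false-positive rates. They need another reason for outcome-related loss in one arm, such as tolerability-related drop-out by participants whose CIMT would have run a different course. Blinding does not exclude that, but no document shows it.

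Three stronger readings are tempting, and the documents support none of them.
- A reader might infer that any significant result below 0.10 mm is fragile. Under loss of benefit, 0.08 mm already holds at 20% missing.
- A reader might infer that, with missing atorvastatin outcomes imputed as placebo-like, a result must reach about 0.075 mm (0.060/0.8) to stay significant. That depends on the variance method. The estimate is 0.8 × observed, and its sampling SE is also 0.8 × 0.030 = 0.024, which leaves the threshold at 0.060. Rubin's rules keep the SE near 0.030 (mean 0.0296 in simulation) and rejected a true null only about 1.8% of the time.
- A reader might infer that sections 4.6.3, 4.13 and 6.2 contradict one another. They can coexist, since section 9.6 separates stopping treatment from leaving the study. What is missing is a statement of whether those who stop drug are scanned at week 48.

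Finally, section 9.6 records interruptions of treatment and follow-up, so with drop-out counts by arm a reader could bound the bias as f × D. That helps, but section 6.2.3 promises no counts by arm and does not replace a pre-specified analysis.

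**Conclusion.** The concern holds as a gap in specification with a modest likely effect, and should be corrected. The rule is invalid by the definition of missing at random, and nothing else in the document supplies a method for missing week-48 CIMT or a sensitivity analysis. That part rests on no numerical assumption, apart from reading the t-test as using observed week-48 values only, which the document implies but does not state.

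The size rests on assumed drop-out patterns. With similar selection in both arms, rejection under no effect stays at about 5% to 7%. In the one-arm extreme at 20% missing, bias is 0.010 to 0.024 mm and false positives about 7% to 14%. If the only difference is loss of benefit, a result at the 0.10 mm design effect is robust, and mainly results between the 0.060 mm threshold and about 0.07 mm are sensitive at 20% missing. Less loss narrows that band.

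**What to change.** - **Section 6.2.3.** Delete the conditional rule. Keep the drop-out comparison, with numbers and reasons by arm, as description only. State in advance that the working assumption is missing at random given arm and observed data.
- **Section 6.2.1.** Replace the t-test with a model of week-48 CIMT change adjusted for baseline CIMT. This improves precision; it does not by itself recover participants without a week-48 value.
- **Sensitivity analysis.** Pre-specify one delta analysis that shifts missing atorvastatin outcomes up to the tipping point. If placebo-like imputation is preferred, state the variance method, because Rubin's rules are conservative there.
- **If multiple imputation is used.** Name the variables: arm, baseline CIMT, age, sex, screening LDL, week-24 lipids and biomarkers where available, and adherence up to drop-out. Section 4.11.2 already collects the last: "In the end of every month, each participant should return the unused pills every month".
- **Clarification.** Reconcile sections 4.6.3, 4.13, 6.2 and 9.6 on whether participants who stop study drug still have a week-48 CIMT and are analysed as randomised.

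The cost is SAP wording and a little more analysis, with no new data for the model. The sensitivity estimate may be less favourable. If the clarification keeps those who stop drug in follow-up, there are a few more week-48 scans: at most 0.20 × 80 = 16 at the planned allowance.
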